#### Von Frey hair filament assessment

Von Frey hair filament assessment on capsaicin treated skin will only be performed on subjects who are not allergic or intolerable to the capsaicin solution as confirmed at screening. At screening and prior to dosing on each treatment day, it will be evaluated which Von Frey filament is felt as 'nearly painful' using a set of 128 mN, 256 mN and 512 mN filaments, just outside the area to be stimulated. This filament will be used during the treatment day to determine the secondary mechanical allodynic area. From the centre of the primary area, eight spokes (each 45°) dividing an octagon in equal parts will be drawn. On the two lateral-medial spokes 8 points and on the six remaining spokes 9 points, each 5mm apart, will be the designated Von Frey hair stimulation location. Stimulation method will be starting from the stimulation point furthest away towards the middle. Once a change in sensation is felt, from nearly painful to painful, that point is determined to be the border of the secondary allodynic area. The area is determined by connecting the allodynic points to span an octagon. To minimize the risk of measuring false positive central sensitization, the primary area will be surrounded by a border of 5 mm, in which no secondary mechanical allodynia measurements will be performed.

#### Endpoint:

 Area of secondary mechanical allodynia (mm²) using Von Frey hairs (volar forearm only for capsaicin eligible subjects).

[figure not shown]

Figure 2. Visualization Von Frey hair filament assessment

Heat pain assessment (normal skin, and capsaicin exposed skin)

Thermal PDTs are determined using a thermode (Medoc Q-Sense, Israel, contact area: 30mm x 30mm), that is placed on the subject's back. The initial temperature of the thermode is 32 °C and gradually increases in temperature with 0.5 °C/s, until the subject perceives the stimulus as painful (pain detection threshold, PDT), or if a temperature of 50 °C is reached. The subject indicates his PDT by pushing the button on a hand-held feedback control. The average of a triplicate measurement is used for further analysis.

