- Follow up (FU) visit after last treatment.
- Only weight will be measured at FU or upon early termination
- Physical examination at screening includes assessment of the Fitzpatrick skin type and evaluation of acne, freckles, tattoos or scarring on the back.
- A symptoms based physical examination will be performed.
- For women of childbearing potential: Urine beta HCG will be performed either during screening, on the first day of each treatment period or the day before the first day of each
- Treatment Period at discretion of Investigator. In either case, the results must be negative prior to dosing study participants.

  Vital signs will be measured in supine position. Oxygen saturation will be monitored after dosing at 2h until the end of study day 1 of each treatment period.
- Lunch at 0.5h and dinner 8h post dose, snack at 4.5h, time points are indicative. Light breakfast on Day 1 is shortly after wake activity around -3.5hours, after breakfast the subject starts fasting until after dosing. No meal restrictions on day -1 and day 2.
- PK sample taken 3 minutes after dosing
- Capsaicin application at screening must be performed on or before Day -5 to ensure sufficient washout between the capsaicin that is applied at screening and applied on Day 1.
- Capsaicin application will only be performed after enrolment in subjects not allergic or intolerable to the capsaicin solution, as determined at screening
- Sequence of assessments is NeuroCart® before PainCart®, for specific order of assessments see section 6.4.

  Capsaicin heat pain test (and heat pain test on control skin on volar forearm) will only be performed on subjects not allergic or intolerable to the capsaicin solution. Capsaicin heat pain task only applicable for Day 1.

  PainCart® training up to 42 days before dosing and NeuroCart® training up to 21 days before dosing.
- PainCart® and NeuroCart® will be done twice for baseline measurement
- NeuroCart® round with pEEG measurement only in second baseline measurement
- VVLT at 2u post dose will be measured is the immediate recall. VVLT at 5u post dose will be the delayed recall and recognition.
- Discharge time is approximate and only when deemed safe.

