#### Capsaicin 1% application

Capsaicin application and related tests (heat pain test on capsaicin-treated skin and control skin on contralateral arm, and Von Frey test) will only be performed for subjects found eligible at screening (i.e., not to be allergic and/or tolerable to the capsaicin solution). Subjects allergic and/or intolerable to the capsaicin solution may participate in the trial; no capsaicin-related measurements will be performed for them.

The capsaicin 1% model is included as a model for heat and mechanical allodynia. Capsaicin is applied during screening procedures, to evaluate whether subjects are allergic to the solution, and applied 60 minutes prior to study drug administration. A 3x3 cm surface on the dominant volar forearm is used as application site; the non-dominant volar forearm serves as a non-stimulated control. At 30 minutes post-application, abundant solution is wiped off towards the centre of the application site, if necessary. Immediately after, and subsequently at given time points, Von Frey hair filament assessments and heat pain tests are performed on the 3x3 cm area.

Capsaicin application and related tests (heat pain test on capsaicin-treated skin and control skin on contralateral arm, and Von Frey test) will only be performed for subjects found eligible at screening (i.e., not to be allergic and/or tolerable to the capsaicin solution). Subjects allergic and/or intolerable to the capsaicin solution may participate in the trial; no capsaicin-related measurements will be performed for them.

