#### **Endpoint**

- Heat pain (pre-cold pressor test): capsaicin treated area PDT (°C), and post-test VAS (mm) (volar forearm only for capsaicin eligible subjects).
- Heat pain (pre-cold pressor test): control area PDT (°C), and post-test VAS (mm).

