## Cold pressor pain assessment

The method of cold pressor pain is based on the methods described by Eckhardt et~al. and Jones et~al. 33,34 Subjects place their non-dominant hand into a water bath (minimal depth 200 mm) at 35  $\pm$  0.5 °C for 2 minutes. At 1 minute 45 seconds, a blood pressure cuff on the upper-arm will be inflated to 20 mmHg below resting diastolic pressure. At 2 minutes the subject will then move their hand from the

warm water bath, directly placing their hand into a similar sized bath at  $1.0 \pm 0.5$  °C. The subjects will be instructed to indicate when PDT is reached (first change in sensation from cold non painful to painful) as well as the increase in pain intensity, by moving the eVAS slider. When PTT is reached (sensation is no longer tolerable; eVAS slider at 100mm), or when a time limit (120s) is reached, subjects are instructed to remove their hand from the water, at which point the blood pressure cuff will deflate.

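### The heat-pain procedure places the thermode on the back, while the capsaicin and control skin are on the volar forearms; this conflicts for capsaicin heat and leaves two competing sites for control heat and CPM

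*Protocol*

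**What the plan says.** The heat-pain procedure in Protocol section 2.10.3 is headed "Heat pain assessment (normal skin, and capsaicin exposed skin", so it covers both skin types. It describes a 30 mm x 30 mm thermode "that is placed on the subject's back" and gives no other location.

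The capsaicin section, also in 2.10.3, says: "A 3x3 cm surface on the dominant volar forearm is used as application site", and "the non-dominant volar forearm serves as a non-stimulated control". It adds that "Von Frey hair filament assessments and heat pain tests are performed on the 3x3 cm area". The endpoint list after the heat-pain procedure defines the capsaicin measure as "capsaicin treated area PDT (°C), and post-test VAS (mm) (volar forearm only for capsaicin eligible subjects". The companion control-heat endpoint refers only to a control area.

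For CPM, section 2.10.3 defines the response as the change in heat pain on unexposed or normal skin from before to after the cold pressor, and names no body site. On the cold pressor itself it says: "Subjects place their non-dominant hand into a water bath". That bath is at 1.0 ± 0.5 °C, and a cuff on the upper arm is inflated during the test.

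The footnotes to Table 1 put the control-skin heat test on the volar forearm, but the screening examination includes "evaluation of acne, freckles, tattoos or scarring on the back". Exclusion criterion 22 (section 2.6.3) names the volar forearm as the area of interest for skin type, acne, tattoos and scarring.

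**The concern.** This text tells staff where to put the probe for endpoints that Table 2 lists under the primary objective, so a wrong or open site changes what is measured. Three things are at stake.

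- **Capsaicin heat.** Nothing is applied to the back. A reading taken there cannot show a drug effect on sensitised skin.
- **CPM.** The section presents CPM as a measure of central descending inhibition. If the test site is the forearm above the hand that has just left the bath, local cooling or the cuff could also shift the heat threshold. This is an assumption, since the protocol gives no figure for forearm cooling or its effect on heat PDT.
- **Who contributes.** Heat testing of control skin on the contralateral arm is restricted to capsaicin-eligible subjects. Table 2 puts no such restriction on CPM.

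**Working it through.** The protocol states no figure on this point, so the check sets the passages side by side.

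| Place in the protocol | What it locates | Site |
|---|---|---|
| 2.10.3, heat-pain procedure | thermode, normal and capsaicin skin | back |
| 2.10.3, capsaicin application | treated skin | dominant volar forearm |
| 2.10.3, capsaicin application | control skin | non-dominant volar forearm |
| 2.10.3, capsaicin application | heat tests after application | the treated 3x3 cm area |
| 2.10.3, heat endpoints | capsaicin heat | volar forearm |
| 2.10.3, heat endpoints | control heat | control area, no body site |
| Table 1 footnote | control-skin heat test | volar forearm |
| Table 1 footnote | screening skin check | back |
| 2.6.3, criterion 22 | area of interest | volar forearm |
| 2.10.3 CPM and 2.10.4 | normal-skin heat tests | no body site |
| 2.10.3, cold pressor | immersed limb | non-dominant hand |

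**Capsaicin heat.** Every passage that locates the treated skin puts it on the forearm. The thermode face (30 mm x 30 mm = 9 cm²) equals the treated area (3 cm x 3 cm = 9 cm²), which fits a test on that area. Only the procedure says the back. It conflicts with the rest and cannot be carried out on treated skin.

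**Control heat.** The capsaicin section and the Table 1 footnote favour the volar forearm, specifically the non-dominant one. The procedure, whose heading includes normal skin, says the back. The endpoint line does not settle it.

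**CPM.** The definition relies on the heat test on unexposed or normal skin, so it inherits both candidates:

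1. *Non-dominant forearm.* This is the immersed limb. The capsaicin section and the Table 1 footnote limit arm control-skin testing to capsaicin-eligible subjects, so ineligible subjects would have no CPM value.
2. *Back.* This is away from the immersed limb and available to every subject.

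The set of subjects with CPM data therefore depends on an unstated choice.

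**Scheduling.** The sequence in 2.10.4 starts PainCart with heat pain on normal and capsaicin skin. It later lists a separate normal-skin heat test directly before the cold pressor and another after it. The CPM pair is already in the schedule; only its site is missing.

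**Extent.** First-round PainCart entries in Table 9 are pressure 2, heat 1, cold pressor 2, electrical stair 2, electrical burst 2 and CPM 1: 2 + 1 + 2 + 2 + 2 + 1 = 10. Counting heat PDT separately on normal and capsaicin skin gives 10 + 1 = 11, of which 3 depend on the site. In the second round, VAS and McGill depend on it for heat pain only, because Table 9 gives CPM no second round.

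**The case against.** The strongest reply is that the intent is clear and one stray clause is being over-read. The capsaicin section directs heat tests to the treated area, the endpoint names the volar forearm, and the heading of the heat-pain procedure itself refers to capsaicin-exposed skin, which cannot be the back. Criterion 22 already ties eligibility to the forearm. That stands. A reader might infer that the protocol as a whole takes the capsaicin-heat endpoint on untreated skin; the documents do not support that. They give conflicting sites, with the procedure as the outlier.

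It can also be said that the site is unlikely to drift within a subject. The study is single-centre, and PainCart runs under a named SOP that is not available here. Nothing in the protocol shows that staff would change site between periods, so that possibility is a reason to fix the site in writing, not an expected bias.

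Finally, the CPM concern is conditional: it arises only if the forearm is used, and the hand rather than the forearm is immersed. The size of any local effect is unknown. What remains is that the protocol does not say which site applies, and no reading of it settles the matter for CPM.

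The study is described as exploratory with no formal null hypothesis, which limits the inferential consequence. It does not make a misplaced measurement informative.

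**Conclusion.** The contradiction is real and should be corrected before dosing starts. For capsaicin heat it is a conflict with a clear outlier. For control heat and CPM, two sites compete; a reader might call the CPM site wholly undefined, but the text does supply two candidates. Affected are heat PDT on normal and capsaicin skin with its VAS and McGill scores, and CPM PDT alone. The sample size, which rests on cold pressor PTT, does not change.

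The capsaicin conclusion and the effect on who has CPM data follow from the text. Only the possible mixing of local cooling or cuff effects with the CPM response rests on an assumption that the documents do not quantify.

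**What to change.** In the heat-pain procedure of section 2.10.3, replace the single site with one site per test:

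- **Capsaicin heat:** the treated area on the dominant volar forearm.
- **Control heat:** the contralateral volar forearm, as the capsaicin section and the Table 1 footnote already have it.
- **CPM pair:** one normal-skin site off the cold-pressor limb, the same before and after the bath. State that it applies to all subjects, including those not eligible for capsaicin, and repeat the site in the CPM section and in 2.10.4.

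State that the same sites are used in both periods. Align the screening skin check in the Table 1 footnote with criterion 22 and with the sites chosen.

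The cost is protocol wording. Because 2.10.4 already lists a separate normal-skin heat test on each side of the cold pressor, no additional heat reading is needed.

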#### **Endpoint**

- Heat pain (pre-cold pressor test): capsaicin treated area PDT (°C), and post-test VAS (mm) (volar forearm only for capsaicin eligible subjects).
- Heat pain (pre-cold pressor test): control area PDT (°C), and post-test VAS (mm).

#### Pressure pain assessment

This method of pressure pain induction has been shown to primarily assess nociception generated from the muscle with minimal contribution by cutaneous nociceptors . Briefly, an 11 cm wide tourniquet cuff (VBM Medizintechnik GmbH, Sulz, Germany) will be placed over the gastrocnemius muscle with a constant pressure rate increase of 0.5 kPa/s controlled by an electro-pneumatic regulator (ITV1030-31F2N3-Q, SMC Corporation, Tokyo, Japan), Power1401mkII analogue—to-digital converter and Spike2 software (CED, Cambridge, UK). The subject will sit comfortably with their foot flat on the floor and rate their pain intensity using the eVAS, with 0 and 100 defined as "no pain" and "worst pain tolerable", respectively. eVAS > 0 is used as PDT. The pneumatic pressure will be increased until the subject indicates their PTT, or a maximum pressure of 100 kPa is achieved, at which point the device releases pressure to the tourniquet.

## **Endpoints:**

• Pressure pain: PDT (kPa), PTT (kPa), Area Under the VAS pain Curve (AUC) (kPa\*mm), and post-test VAS (mm).

## Cold pressor pain assessment

The method of cold pressor pain is based on the methods described by Eckhardt et~al. and Jones et~al. 33,34 Subjects place their non-dominant hand into a water bath (minimal depth 200 mm) at 35  $\pm$  0.5 °C for 2 minutes. At 1 minute 45 seconds, a blood pressure cuff on the upper-arm will be inflated to 20 mmHg below resting diastolic pressure. At 2 minutes the subject will then move their hand from the

warm water bath, directly placing their hand into a similar sized bath at  $1.0 \pm 0.5$  °C. The subjects will be instructed to indicate when PDT is reached (first change in sensation from cold non painful to painful) as well as the increase in pain intensity, by moving the eVAS slider. When PTT is reached (sensation is no longer tolerable; eVAS slider at 100mm), or when a time limit (120s) is reached, subjects are instructed to remove their hand from the water, at which point the blood pressure cuff will deflate.

## **Endpoints:**

• Cold pressor: PDT (s), PTT (s), AAC (s\*mm), and post-test VAS (mm).

## Electrical Stimulation assessment (Electrical Burst and Stair)

For cutaneous electrical pain, two electrodes (Ag-AgCl) are placed on clean (scrubbed) and if required, shaved skin overlying the left tibial bone 100 mm distal from the caudal end of the patella; middle of the first electrode is placed 100 mm distal the caudal end of the patella and middle of the second electrode directly (±135 mm) underneath the first. For single stimulus (electrical stair pain test), each sole stimulus (10 Hz tetanic pulse with a duration of 0.2 ms) is controlled by a constant current stimulator. Current intensity increases from 0 mA in steps of 0.5 mA·s-1 (cutoff 50 mA).

For repeated stimulus (electrical burst pain test), each single stimulus (train of five, 1 ms square wave pulses repeated at 200 Hz) is repeated 5 times with a frequency of 2 Hz at the same current intensity with a random interval of 3 to 8 seconds between the repetitions. Current intensity increases from 0 mA in steps of 0.5 mA (cutoff 50 mA). PDT is taken as the value (mA) whereby a subject indicates either: all 5 stimuli are painful, or the train of 5 stimuli started feeling non-painful but ends feeling painful  $(VAS > 0)^{35}$ . The pain intensity will be measured using the eVAS, until PTT (eVAS = 100) is reached, or a maximum of 50 mA is reached.

#### **Endpoints:**

- Electrical Burst: PDT (mA), PTT (mA), AUC (mA\*mm), and post-test VAS (mm).
- Electrical Stair: PDT (mA), PTT (mA), AUC (mA\*mm), and post-test VAS (mm).

#### Conditioned Pain Modulation (CPM)

Effects on the centrally acting descending inhibitory control pathway are measured using the conditioned pain modulation (CPM) response, which is quantified by calculating the difference of pain detection and pain tolerance threshold of the heat pain test on unexposed/normal skin, directly after the cold pressor pain test, and the heat pain detection and tolerance thresholds prior to the cold pressor pain test.

## **Endpoints:**

• Conditioned Pain Modulation Response (change from heat pain on unexposed/normal skin pre- and post-cold pressor): PDT (°C).

## Subjective (pain) perception

The subject is asked to rate their pain after the heat-, cold pressor-, electrical-, and pressure pain tests using a digital, amended, Dutch language version of the short form of the McGill pain questionnaire (SF-MPQ). The questionnaire consists of:

- 16 questions regarding type of pain experienced measured with a 4-point Likert -type scale). From these measurements, two main factors are the calculated as described by Melzack: sensory (from 11 scores) affective (from 4 scores).
- A choice of one of 5 descriptors measuring peak pain intensity of the test just performed.

#### **Endpoints:**

McGill Pain Questionnaire (score)

# NeuroCart® (see CHDR SOP CCNNCART)

The NeuroCart® will include pEEG (at applicable timepoints), Saccadic eye movement, Smooth pursuit eye movement, Pupillometry, Adaptive tracking, Bond & Lader, Bowdle, N-Back, VVLT, Body Sway, STAI. These measurements will be conducted according to CHDR standard operating procedures. One NeuroCart® round will take ±40 minutes.

Saccadic eye movement & Smooth pursuit eye movement

Analysis of smooth pursuit and saccadic eye movements are frequently used for the assessment of (side) effects of drugs involving the central nervous system. The use of a computer for measurement of saccadic eye movements was originally described by Baloh *et al.*. and for smooth pursuit by Bittencourt *et al.* and has been extensively validated at the CHDR by Van Steveninck *et al.*

## Saccadic eye movement

Saccadic peak velocity is one of the most sensitive parameters for sedation. The use of a computer for measurement of saccadic eye movements was originally described by Baloh et al., and has been validated at CHDR by Van Steveninck et al. While the sedative effects of 20 mg oral temazepam were detectable by subject self-report, visual analogue scales and SEM testing, at a dose of 5 mg were only detectable with measures of SEM. The effects of 1 night of sleep deprivation (suggested as a threshold level of clinically significant sedation) were consistently detectable by SEM testing with a sustained decrease in saccadic peak velocity of 9 to 10% observed.

Saccadic eye movements will be recorded at a training session, pre-dose and at times specified in the protocol. Recording of eye movements will be performed in a quiet room with dimmed lightning. There will be only one subject per session in the same room.

Disposable silver-silver chloride electrodes (Ambu Blue Sensor N) will be applied on the forehead and beside the lateral canthi of both eyes of the subject for registration of the electro-oculographic signals. Skin resistance is reduced to less than 5 kOhm before measurements. Head movements are restrained using a fixed head support. The target consists of a moving dot that is displayed on a computer screen. This screen is fixed at 58 cm in front of the head support.

Saccadic eye movements are recorded for stimulus amplitudes of approximately 15 degrees to either side. Fifteen saccades are recorded with interstimulus intervals varying randomly between 3 and 6 seconds. Average values of latency (reaction time), saccadic peak velocity of all correct saccades and inaccuracy of all saccades will be used as parameters. Saccadic inaccuracy is calculated as the absolute value of the difference between the stimulus angle and the corresponding saccade, expressed as a percentage of the stimulus angle.

The measurements of saccadic eye movements will take approximately 2 min.

## Smooth pursuit eye movement

The same system as used for saccadic eye movements is also used for measurement of smooth pursuit. For smooth pursuit eye movements, the target moves at a frequency ranging from 0.3 to 1.1 Hz, by steps of 0.1 Hz. The amplitude of target displacement corresponds to 22.5 degrees eyeball rotation to both sides. Four cycles are recorded for each stimulus frequency. The method has been validated at CHDR by Van Steveninck et al. based on the work of Bittencourt et al.and the original description of Baloh et al.

The time in which the eyes are in smooth pursuit of the target will be calculated for each frequency and expressed as a percentage of stimulus duration. The average percentage of smooth pursuit for all stimulus frequencies will be used as parameter.

This measurement takes approximately 1 minute.

